9.6 Pharmacodynamics

Not applicable per Protocol Amendment 01. The following information refers to the original study design.

Pharmacodynamic parameters will be evaluated in this study. Systemic immune monitoring of MDSCs, cytokines/chemokines, and other related soluble factors to investigate the immunomodulatory properties of nivolumab, ipilimumab, and TACE will be assessed. See Section 9.8 (Biomarkers) for a detailed description of the analyses and [Table 9.8-1](#) for the sample collection schedule.

Please see [Appendix 9](#) for country-specific criteria for the collection and analyses of samples in China.

9.7 Pharmacogenomics

Not applicable.

9.8 Biomarkers

Not applicable per Protocol Amendment 01. The following information refers to the original study design.

A variety of factors that could potentially predict clinical response to nivolumab, ipilimumab, and/or TACE will be investigated in tumor specimens, peripheral blood, and stool taken from all participants as described below. Data from these investigations will be evaluated for association with efficacy endpoints. In addition, analyses of markers in all 3 treatment arms will provide the necessary data to identify and validate biomarkers with predictive vs prognostic value.

A detailed description of each biomarker analysis is described below and a schedule of biomarker sample collections is provided in [Table 9.8-1](#). Tumor tissue, peripheral blood, and a stool sample will be collected prior to therapy. Peripheral blood samples and a stool sample will also be collected at selected timepoints on-treatment. If a biopsy or surgical resection is performed at the time of TTTP by BICR or end of treatment, tumor sample (block or slides) should also be submitted for analysis. If biomarker samples are drawn but study treatment(s) are not administered, samples will be retained. Detailed instructions of the obtaining, processing, labeling, handling, storage and shipment of specimens will be provided in a separate Procedure Manual at the time of study initiation.

Please see [Appendix 9](#) for country-specific criteria for the collection and analyses of samples in China.

Table 9.8-1: CA20974W Biomarker Sampling Schedule All Participants

Study Day of Sample Collection (1 Cycle = 2 weeks)	Serum Biomarkers ^a	Whole Blood DNA ^a	Whole Blood RNA ^a	MDSC ^a	Plasma (ctDNA) ^a	Stool ^b	Tumor ^{c,d}
Screening							X
Cycle 1 Day 1	X	X	X	X	X	X	
Cycle 3 Day 1	X		X	X	X	X	
Cycle 7 Day 1	X			X		X	
Cycle 13 Day 1					X		
Cycle 19 Day 1					X		
Cycle 25 Day 1					X		
Cycle 31 Day 1					X		
Cycle 37 Day 1					X		
Cycle 43 Day 1					X		
Cycle 49 Day 1					X		
Upon TTTP by BICR or EOT	X			X	X		X

Abbreviations: BICR = blinded independent central review; ctDNA = circulating tumor DNA; DNA = deoxyribonucleic acid; EOT = end of treatment; MDSC = myeloid-derived suppressor cells; RNA = ribonucleic acid; TACE = trans-arterial chemoembolization; TTTP = time to TACE progression.

^a Prior to dosing (when applicable).

^b Stool collection is optional and should be collected within 7 days prior to dosing. Stool should not be collected in China and in other geographies if restricted by local requirements.

^c Tumor tissue submission during screening is required for randomization. Upon TTTP by BICR or end of treatment, tumor tissue submission is highly recommended if clinically feasible

^d Biomarker samples will not be collected [REDACTED] except for tumor samples during Screening. See [Appendix 9](#).

9.8.1 Tumor-based Biomarker Measures

Not applicable per Protocol Amendment 01. The following information refers to the original study design.

Tumor tissue will be obtained at baseline and upon TTTP by BICR or end of treatment (if clinically feasible) to characterize immune cell populations, expression of selected tumor markers, expression of inflammatory genes, and genetic analyses mentioned below in detail. Tumor block (preferred) or slides must be sent to the central laboratory prior to randomization. Biopsy samples should be excisional, incisional, or core needle. Fine needle aspirates or other cytology samples are not acceptable. A tumor block is preferred, but if a block is not feasible, a minimum of 20 unstained slides is required. Slides should be unstained, have a recommended tissue section thickness of 4 microns, and must be positively charged. Tumor tissue must contain adequate tumor content (≥ 100 tumor cells), as determined by hematoxylin and eosin (H&E) review at the central laboratory. If the initial tumor sample submission does not meet this criterion, an additional tissue submission (if available) is allowed. Participants must have an evaluable tumor tissue specimen to be eligible for randomization. A tumor biopsy upon TTTP by BICR or end of treatment is also highly recommended, if clinically feasible.

Tumor samples may be used for the assessments described below. Please see [Appendix 9](#) for country-specific criteria for the collection and analyses of tumor-tissue samples in China.

9.8.1.1 Characterization of Tumor Infiltrating Lymphocytes and Tumor Antigens

Not applicable per Protocol Amendment 01. The following information refers to the original study design.

Immunohistochemistry (IHC) may be used to assess tumor markers as well as the number and composition of immune infiltrates in order to define the immune cell subsets present within FFPE tumor tissue before therapy and upon TTTP by BICR or end of treatment. IHC analyses may include, but not necessarily be limited to, the following markers: major histocompatibility complex (MHC) class I/II, CD8, PD-1, PD-L1, PD-L2, and lymphocyte activating 3 (LAG3).

9.8.1.2 Tumor Genomic Analysis Including Tumor Mutational Burden and Gene Expression Analysis

Not applicable per Protocol Amendment 01. The following information refers to the original study design.

DNA from tumor samples will be analyzed using platforms, including, but not limited to, whole-exome sequencing to identify and quantify somatic mutations by using the whole blood DNA sample as a germline reference. Mutations that are detected may be analyzed for their ability to bind the MHC class I and MHC class II proteins using prediction algorithms. Evaluating the ability of tumor mutations to bind MHC molecules may provide evidence that these mutations are serving as antigens that are recognized by the immune system and are potential rejection antigens. MSI or MSI status may be derived from whole-exome sequencing data if MSI status is not already known. Lastly, RNA expression within tumor biopsies may be examined using RNAseq, whole-

transcriptome sequencing, or other next-generation sequencing technologies to detect expression of all genes.

9.8.2 Peripheral Biomarkers

9.8.2.1 Myeloid-derived Suppressor Cells

Not applicable per Protocol Amendment 01. The following information refers to the original study design.

MDSCs are an immune cell population capable of suppressing T cell activation and proliferation. MDSCs will be measured prior to dosing on Cycle 1 Day 1, on-treatment, and upon TTTP by BICR or end of treatment to assess pharmacodynamic changes as well as associations with outcome.

9.8.2.2 Soluble Biomarkers and Other Assessments in Serum

Not applicable per Protocol Amendment 01. The following information refers to the original study design.

Serum will be collected prior to dosing on Cycle 1 Day 1, on-treatment, and upon TTTP by BICR or end of treatment to measure levels of cytokines, chemokines, other immune mediators, and extracellular matrix fragments. These factors will be assessed by techniques that may include, but are not limited to, enzyme-linked immunosorbent assay (ELISA) or multiplex assays. Analyses may include, but are not limited to, IFN- γ , C-X-C motif chemokine ligand (CXCL) 9, CXCL10, soluble PD-L1, collagen, and other extracellular matrix fragments. These analyses may identify potential biomarkers with prognostic and predictive value for outcomes.

9.8.2.3 Genomic Analysis of Circulating Tumor DNA in Plasma

Not applicable per Protocol Amendment 01. The following information refers to the original study design.

Plasma will be collected prior to dosing on Cycle 1 Day 1, on-treatment, and upon TTTP by BICR or end of treatment to enable genomic analysis of circulating tumor DNA (ctDNA).

9.8.2.4 Whole Blood DNA and RNA Analyses

Not applicable per Protocol Amendment 01. The following information refers to the original study design.

DNA in the whole blood samples may be used to examine germline (predisposing) characteristics as well as to help identify genetic information specific to the participant's tumor, such as somatic DNA alterations. RNA in the whole blood sample may be used to assess the expression of genes associated with inflammation. These blood samples will be obtained prior to dosing on Cycle 1 Day 1 (whole blood DNA and whole blood RNA) and on-treatment (whole blood RNA only) unless restricted by local requirements.

9.8.2.5 Viral Safety Biomarkers

At screening, HBV DNA, qualitative and quantitative hepatitis B surface antigen (qHBsAg), hepatitis B e-antigen (qHBeAg), hepatitis B surface antibody (HBsAb), HCV RNA,

HCV antibody, and hepatitis D antibody (if chronic HBV infection) samples will be collected for all participants. On-treatment and during follow-up visits FU1 and FU2, HBV DNA will only be collected for HBV chronic-infected participants, and HCV RNA will only be collected for HCV chronic-infected participants. Details regarding sample collection timepoints can be found in [Section 2](#) (Schedule of Activities). These analyses will be performed at the central laboratory. Results of HBV DNA and HCV RNA will be provided to sites for management of virologic breakthrough (see [Section 7.7.3.1](#) [Antiviral Therapy]).

9.8.3 Microbiome Analysis

Not applicable per Protocol Amendment 01. The following information refers to the original study design.

An optional stool sample will be collected prior to dosing and while on-treatment to assess microbiome diversity and composition, unless restricted by local requirements.

9.8.4 Additional Research Collection

Not applicable per Protocol Amendment 01. The following information refers to the original study design.

This protocol will include residual sample storage for additional research (AR).

For All US sites:

AR is required for all study participants, except where prohibited by IRBs/ethics committees, or academic/institutional requirements. Where 1 or more of these exceptions occurs, participation in the AR should be encouraged but will not be a condition of overall study participation.

- If the IRB/ethics committees and site agree to the mandatory AR retention and/or collection, then the study participant must agree to the mandatory AR as a requirement for inclusion in the study.
- If optional participation is permitted and approved, then the study participants may opt out of the additional AR and/or collection.

For non-US Sites

AR is optional for all study participants, except where retention and/or collection is prohibited by local laws or regulations, ethics committees, or institutional requirements.

This collection for AR is intended to expand the translational R&D capability at BMS, and will support as yet undefined research aims that will advance our understanding of disease and options for treatment. It may also be used to support health authority requests for analysis, and advancement of pharmacodiagnostic development to better target drugs to the right patients. This may also include genetic/genomic exploration aimed at exploring disease pathways, progression and response to treatment, etc.

Sample Collection and Storage

All requests for access to samples or data for AR will be vetted through a diverse committee of the study Sponsor’s senior leaders in R&D (or designee) to ensure the research supports appropriate and well-defined scientific research activities.

- Residual PK/IMG, tumor tissue, and serum, plasma, whole blood, and stool samples from collections (see Table 9.8.4-1 [Residual Sample Retention for Additional Research Schedule]) will also be retained for AR purposes.

Samples kept for future research will be stored at the BMS Biorepository in [REDACTED] or an independent, BMS-approved storage vendor.

The manager of these samples will ensure they are properly used throughout their usable life and will destroy the samples at the end of the scheduled storage period, no longer than fifteen (15) years after the end of the study or the maximum allowed by applicable law.

Transfers of samples by the research Sponsor to third parties will be subject to the recipient’s agreement to establish similar storage procedures.

Samples will be stored in a coded fashion, and no researcher will have access to the key. The key is securely held by the Investigator at the clinical site, so there is no direct ability for a researcher to connect a sample to a specific individual.

Further details of sample collection and processing will be provided to the site in the Procedure Manual.

Table 9.8.4-1: Residual Sample Retention for Additional Research Schedule

Sample Type	Timepoints for Which Residual Samples will be Retained
PK/IMG	All
Tumor tissue	All
Serum biomarkers	All
Plasma for ctDNA	All
Whole blood DNA	C1D1
Whole blood RNA	C1D1
Stool	All

Abbreviations: C = cycle; ctDNA = circulating tumor DNA; D = day; DNA = deoxyribonucleic acid; IMG = immunogenicity; PK = pharmacokinetics; RNA = ribonucleic acid.

9.9 Health Economics OR Medical Resource Utilization and Health Economics

Not applicable per Protocol Amendment 01. The following information refers to the original study design.

Healthcare resource utilization (HCRU) data will be collected for all randomized participants using an internal CRF developed for use in previous trials. The form, which is completed by study staff, records information about hospital admissions, including number of days spent in various wards and discharge diagnosis, as well as non-protocol specified visits related to study therapy, including date of visit, reason for visit, and type of visit. The HCRU data will be used to support subsequent economic evaluations.

10 STATISTICAL CONSIDERATIONS

Per Protocol Amendment 01, only safety analyses will be conducted. Summary tables and listings for baseline, disposition, and safety data will be provided to support the Clinical Study Report (CSR) and study data disclosure. Listings for efficacy data may be provided, if requested, per regional data disclosure requirement. Details of the analysis and outputs will be provided in the SAP.

10.1 Sample Size Determination

Per Protocol Amendment 01, sample size will be limited to the participants randomized as of 22-Sep-2021. The following information refers to the original study design.

For the comparison of nivolumab and ipilimumab plus TACE (Arm A) vs nivolumab placebo and ipilimumab placebo plus TACE (Arm C), both TTTP and OS are primary endpoints. For sample size determination purpose, the family-wise error rate of 5% will be controlled using Bonferroni split: comparison of TTTP with alpha of 1% and comparison of OS with alpha of 4%.

Approximately 765 participants will be randomized to 3 treatment arms in a 1:1:1 ratio in approximately 36 months. Approximately 94% and 89% power will be achieved for TTTP and OS, respectively, under the detailed assumptions described in following subsections. EAST v6.4.1 was used to conduct simulations for sample size calculation.

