3.1.1 Research Hypothesis

Not applicable per Protocol Amendment 01. The following information refers to the original study design.

Treatment with nivolumab and ipilimumab or nivolumab in combination with trans-arterial chemoembolization (TACE) will improve time to TACE progression (TTTP) and/or overall survival (OS) compared to TACE in participants with intermediate stage HCC.

3.1.2 Changes Per Protocol Amendment 01

 Therefore, a decision was made by Bristol-Myers Squibb (BMS) in September 2021 to stop the study. Importantly, there is no change to the understanding of the safety profile of nivolumab alone or in combination with ipilimumab and TACE for the treatment of patients with intermediate-stage HCC.

As of 22-Sep-2021, the following measures were put into effect:

- Enrollment of new participants was closed.
- Participants who signed study consent prior to this notification and were undergoing screening were permitted to be randomized to study treatment.
- Participants currently on treatment were allowed to continue study treatment.

- For participants currently in survival follow-up, it is at the discretion of the investigator and participant whether to continue follow-up until Protocol Amendment 01 is approved by the relevant Health Authorities and Institutional Review Boards (IRBs)/Independent Ethics Committees (IECs) at the site.

Protocol Amendment 01 describes the modification to study procedures. All participants must be re-consented upon approval and implementation of Protocol Amendment 01. These changes affect all participants and should be implemented when Protocol Amendment 01 is implemented at the site.

Key changes in Protocol Amendment 01 include:

- Details of closure of the study, with provision for participants currently on treatment or in the follow-up period to continue in the study per the current protocol amendment.
- The study will be unblinded.
- Removal of placebo infusions for participants in Arms B and C.
- Removal of pharmacokinetic (PK), immunogenicity (IMG), biomarker, and patient-reported outcome (PRO) assessments. **Only safety assessments will be conducted.**
- Removal of on-study imaging assessments. Sites should continue imaging assessments per local standard of care.
- Removal of study-related efficacy assessments. Sites should continue efficacy assessments per local standard of care.

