4 OBJECTIVES AND ENDPOINTS

Per Protocol Amendment 01, no analyses of efficacy, quality of life (QoL)/PROs, healthcare resource utilization, PK, or IMG are planned. Only safety assessments will be conducted. Previously collected biomarker samples may be analyzed, but no further biomarker collections are planned with this amended protocol.

Table 4-1: Objectives and Endpoints

Objective	Endpoint

To evaluate the safety and tolerability of Arm A, Arm B, and Arm C in all treated participants.	
Incidence of AEs, SAEs, deaths, AEs leading to discontinuation, and laboratory abnormalities in all treated participants.

Abbreviations: AE = adverse event; SAE = serious adverse event.

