5.1.5 Data Monitoring Committee and Other External Committees

5.1.5.1 Data Monitoring Committee

A DMC will be established to provide oversight and safety and efficacy considerations in the CA20974W study. On 22-Sep-2021, enrollment was closed and a total of 26 participants have been randomized. The DMC will provide advice to the Sponsor regarding actions the committee deems necessary for the continuing protection of participants enrolled/treated in the study. The DMC will be charged with assessing such actions in light of an acceptable benefit-risk profile for nivolumab and ipilimumab or nivolumab in combination with TACE. A safety review will be conducted by the DMC after all participants have been randomized and have been followed for a minimum of 6 weeks, unless decided otherwise by the DMC chair. After participants are unblinded as per Protocol Amendment 01, the Sponsor will continue safety monitoring of remaining participants on the study. No subsequent DMC meeting will occur after the first safety monitoring meeting.

The BMS clinical study leadership will have responsibility for the overall conduct of the study, including managing the communication of study data. The group will be responsible for promptly reviewing the DMC recommendations, providing guidance regarding the continuation or termination of the study, and determining whether amendments to the protocol or changes to the study conduct are required.

Details of the DMC responsibilities and procedures will be specified in the DMC Charter.

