5.2 Number of Participants

As of 22-Sep-2021, enrollment for new participants was closed. The number of participants randomized was 26 as of 14-Oct-2021.

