10.2 Populations for Analyses

Per Protocol Amendment 01, only safety assessments will be conducted.

For purposes of analysis, the following populations are defined in Table 10.2-1.

Table 10.2-1: Populations for Analyses

Population	Description
All Enrolled	All participants who signed an ICF and were registered into the IRT.
All Randomized	All participants who were randomized to any treatment arm in the study. Participants are grouped within the All Randomized population by the treatment to which they were randomized. This is the primary analysis set for demography, protocol deviations, and baseline characteristics.
All Treated	All enrolled participants who receive at least 1 dose of study drug. Participants are grouped within the All Treated population according to the treatment they actually received. This is the analysis set for all safety analyses and study drug administration.
PK	Not applicable per Protocol Amendment 01. All participants who receive at least 1 dose of nivolumab or ipilimumab and have available serum concentration data that allow for computation of meaningful PK parameter values.
IMG	Not applicable per Protocol Amendment 01. All nivolumab- or ipilimumab-treated participants with baseline and at least 1 post-baseline IMG assessment.
Biomarker	Not applicable per Protocol Amendment 01. All Treated participants who have available biomarker data. For predictive biomarkers, biomarker population includes all randomized participants who have biomarker data available at baseline. For pharmacodynamic biomarkers, the biomarker population includes all randomized participants who have baseline and at least 1 post-baseline biomarker data available.

Table 10.2-1: Populations for Analyses

Population	Description
PRO Analysis	Not applicable per Protocol Amendment 01. All Treated participants who have a valid baseline assessment (prior to treatment on Cycle 1 Day 1) and at least 1 post-baseline assessment during the treatment period.

Abbreviations: ICF = informed consent form; IMG = immunogenicity; IRT = interactive response technology; PK = pharmacokinetics; PRO = patient-reported outcome.

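### Does limiting the sample to participants randomized by 22-Sep-2021 remove later-randomized, treated participants from the safety analysis?

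*Combined protocol and SAP*

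**What the plan says.** Amendment 01 stopped the study and reduced it to safety. On the size of the sample, Section 10.1 says: "Per Protocol Amendment 01, sample size will be limited to the participants randomized as of 22-Sep-2021". The rest of that section describes the withdrawn 765-participant design.

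Three other places bear on the date:

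- Section 3.1.2, among the measures effective 22-Sep-2021: "Participants who signed study consent prior to this notification and were undergoing screening were permitted to be randomized to study treatment".
- Section 5.2: "The number of participants randomized was 26 as of 14-Oct-2021". The Synopsis and Section 5.1 give the same number with the same date.
- Section 5.1.5.1, on the data monitoring committee (DMC): "On 22-Sep-2021, enrollment was closed and a total of 26 participants have been randomized".

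The people to be analysed are defined elsewhere. In Table 10.2-1 (Section 10.2), All Treated is "All enrolled participants who receive at least 1 dose of study drug", and its use is stated directly: "This is the analysis set for all safety analyses and study drug administration". All Randomized is "All participants who were randomized to any treatment arm in the study". The single objective in Section 4 is "To evaluate the safety and tolerability of Arm A, Arm B, and Arm C in all treated participants".

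**The concern.** What closed on 22-Sep-2021 was new enrollment. Consented people in screening could be randomized and dosed afterwards, so a sample frozen at those randomized by that date could be smaller than the number treated. The 26 is dated 14-Oct-2021 in most places but stands beside 22-Sep-2021 in Section 5.1.5.1, so a reader cannot tell whether 26 is the Section 10.1 sample or a larger, later count. All of these statements are current Amendment 01 text, so the rule that the amendment overrides conflicting requirements does not choose between them.

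If Section 10.1 were applied as an analysis cut-off, it would drop dosed participants from the only analysis left, and they would be the latest entrants, with the shortest blinded follow-up. In so small a study each one matters. The DMC's safety review, which Section 5.1.5.1 places after all participants have been randomized and followed for at least 6 weeks, might also seem to refer to a different group.

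**Working it through.** No sample-size formula applies, since the sentence concerns a date and a head count. The check is date arithmetic followed by a comparison of definitions.

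**Could anyone have been randomized after the cut-off?** From 22-Sep-2021 to 14-Oct-2021 is 22 days. If a 28-day screening period (Table 2-1, Section 5.1.1) began on 22-Sep-2021, it ends on 20-Oct-2021, 6 days after the count of 26. Later randomization was therefore possible. The 20-Oct date is only illustrative: the 28 days in Section 5.1.1 are counted back from first dose, and Section 9.1.1.3 counts four weeks from screening imaging. Neither sets a randomization deadline from consent.

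**How many?** Let k be the number randomized after 22-Sep-2021. The documents do not give k. Taking the 26 as the full count, Section 10.1 read literally gives 26 − k. The values of k below are assumptions.

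| k | 26 − k | Reduction, k/26 |
|---|---|---|
| 0 | 26 | 0% |
| 1 | 25 | 3.8% |
| 3 | 23 | 11.5% |
| 5 | 21 | 19.2% |

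Section 5.1.5.1 can be read as saying that all 26 were already in on 22-Sep-2021, which would make k = 0 and bring Sections 10.1, 5.2 and 5.1.5.1 into agreement.

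**What would one lost participant do to an arm's event rate?** Arm sizes are not given; 26/3 = 8.7, so assume 8 or 9. With x events in 9, dropping someone without the event moves the rate by x/8 − x/9 = x/72. Dropping someone with it moves the rate by x/9 − (x − 1)/8 = (9 − x)/72. The shift runs from 0 to 8/72 = 11.1 percentage points; for example, going from 5/9 to 4/8 is 4/72 = 5.6 points. For an arm of 8 the denominator is 56 and the maximum is 7/56 = 12.5 points. These maxima arise only if the person dropped is the only one with the event, or the only one without it.

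**Does anyone leave the safety analysis?** Membership of All Treated requires enrollment and one dose. Enrolled, in Table 10.2-1, means consented and registered in the interactive response system. Those covered by the Section 3.1.2 allowance had consented before the notification, and Section 7.2 requires a system number for everyone who consents. They are therefore enrolled on any reading, and once dosed they are in All Treated. No randomization date enters the definition, so the number removed is 0 for every k.

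**Does the DMC review change?** Six weeks (42 days) after a last randomization on 22-Sep, 14-Oct or 20-Oct-2021 is 3-Nov, 25-Nov or 1-Dec-2021. The timing follows the actual last randomization, and the committee chair may decide otherwise. Section 5.1.5.1 does not use the Section 10.1 date.

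**The case for a change.** The best case for acting is that the contradiction is real, sits in current text, and would take a sentence in two or three sections to remove. Amendment 01 was issued on 01-Dec-2021, when a final count should have been available, yet none is labelled final. Section 10.3 leaves the selection of participants for analysis to the SAP, so its author meets one sentence with a date limit and two population definitions without one.

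The mismatch stands: Section 10.1 does not fit Section 3.1.2 or the 14-Oct-2021 date, and the wording in Section 5.1.5.1 is ambiguous. The consequence does not stand. A sentence under sample size determination does not redefine an analysis set, and Table 10.2-1 says which set serves every safety analysis. An analyst following the plan as written would have to ignore that table in order to exclude anyone.

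The probable cause is also harmless. The amendment's summary of changes describes this addition in terms of participants enrolled, not randomized, as of 22-Sep-2021. A difference between the summary and the text is not itself an error, but it points to the intent. Replace the one word with the other and Section 10.1 agrees with Section 3.1.2, because people in screening on that date were already enrolled.

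**Conclusion.** The concern does not call for a change. The plan analyses safety in everyone who received a dose, with no date restriction, so no treated participant is lost whatever the number randomized after 22-Sep-2021. That number is unstated and may be 0. The possible shift of up to 11.1 or 12.5 percentage points per participant is a maximum, on assumed arms of 9 or 8, and would arise only if Section 10.1 were applied in place of Table 10.2-1.

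There are no formal hypotheses, and Section 10 plans summary tables and listings, so the sample-size sentence feeds no power, alpha or test. What is left is a clerical slip in a date or a word, which analysts would resolve from the population table. Aligning the wording would be tidy but would change no result. This conclusion rests on Table 10.2-1 governing the safety analyses, as it says it does.
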